| pcs_e9 | fq2.9 | Parenting confidence at 14 days Q9 | Ordinal | 0=No hardly ever; 1=No, not very often; 2= Yes, some of the time; 3= Yes, most of the time; 4= not applicable |
| pcs_e10 | fq2.10 | Parenting confidence at 14 days Q10 | Ordinal | 0=No hardly ever; 1=No, not very often; 2= Yes, some of the time; 3= Yes, most of the time |
| pcs_e11 | fq2.11 | Parenting confidence at 14 days Q11 | Ordinal | 0=No hardly ever; 1=No, not very often; 2= Yes, some of the time; 3= Yes, most of the time |
| pcs_e12 | fq2.12 | Parenting confidence at 14 days Q12 | Ordinal | 3=No hardly ever; 2=No, not very often; 1= Yes, some of the time; 0= Yes, most of the time |
| pcs_e13 | fq2.13 | Parenting confidence at 14 days Q13 | Ordinal | 0=No hardly ever; 1=No, not very often; 2= Yes, some of the time; 3= Yes, most of the time |
| pcs_e14 | fq2.14 | Parenting confidence at 14 days Q14 | Ordinal | 0=No hardly ever; 1=No, not very often; 2= Yes, some of the time; 3= Yes, most of the time |
| pcs_e15 | fq2.15 | Parenting confidence at 14 days Q15 | Ordinal | 0=No hardly ever; 1=No, not very often; 2= Yes, some of the time; 3= Yes, most of the time |
| gc_end | fq3.1 | Global change at day 14 | Ordinal | 1=completely recovered, 2= much improved, 3= slightly improved, 4= No change, 5= Slightly worse, 6= Much worse, 7= vastly worse |
| ur_reported | fq3.2 | Concerns | Bi-nomial | 0=no, 1=yes |
| ur_typeX | fq3.3 | Concern type | Bi-nomial (7 variables) | 1- more distress 0= no, 1= yes 2- more crying 0= no, 1= yes 3- more unsettled 0= no, 1= yes 4- more vomiting 0= no, 1= yes 5- difficulties feeding 0= no, 1= yes 6- difficulties sleeping 0= no, 1= yes 7- other 0= no, 1= yes |
| ur_type7_txt | fq3.3.1 | Other concerns | Open text | String |
| other_careX | fq3.5 | Other care | Bi-nominal (8 variables) | 1- GP 0= no, 1= yes 2- A&E 0= no, 1= yes 3- unplanned hospital admission 0= no, 1= yes 4- other osteopath 0= no, 1= yes 5- paediatrician 0= no, 1= yes 6- pharmacist 0= no, 1= yes 7- lactation consultant or midwife 0= no, 1= yes 8- other 0= no, 1= yes |
| other_care8_txt | fq3.5.1 | Other care | Open text | String |
| pharmX | fq3.4 | Pharm & Supplements | Bi-nominal (7 variables) | 1- Prescribed medicine 0= no, 1= yes 2- Anti-gas drops 0= no, 1= yes 3- Herbal supplements 0= no, 1= yes 4- Probiotics 0= no, 1= yes 5- Non-cow or ant-allergenic formula milk 0= no, 1= yes 6- Omeprazole 0= no, 1= yes 7- Other 0= no, 1= yes |

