| pharm7_txt | fq3.4.1 | Pharm & Supplements | Open text | String |
| help_belief_end | fq3.6 | Help belief at day 14 | Dichotomous | 0=no, 1=yes |
| experience_end | fq4.1 | Experience at day 14 | Ordinal | 1= very good, 2=fairly good, 3=neither good nor bad, 4=fairly poor, 5=very poor |
| satisfaction_end | fq4.2 | Satisfaction | Ordinal | 1=very satisfied, 2=fairly satisfied, 3=Neither satisfied nor dissatisfied, 4=fairly dissatisfied, 5=very dissatisfied |
| allocation_guess | fq4.3 | Participant's guess about allocation | Nominal | 0=Control treatment (TTR), 1=Test treatment (GTR), 2=Don't know/unsure |

2. Diary and group allocation entries

Dataset name: group.csv (one line per participant)

Source: Castor & Main investigator

Format: csv

- Group allocation is named A and B without the statistician knowing which group is which until after the analysis is complete.
- Per protocol analysis is completed from the detailed description of each deviation.

Details for data format

| Variable | Source | Description | Type | Levels |
|---------------|------------------------|--|-------------|-----------------------------|
| id | diary | UID | Numerical | integer |
| pilot | Data manager | Origin of the data | Dichotomous | 0=Main trial, 1=Pilot phase |
| group | Castor ECD | Group allocation | Dichotomous | Blinded to statistician |
| perprotocol | Participant log | Management was in accordance to protocol | Bi-nomial | 0=No, 1=Yes |
| deviation_txt | Principle investigator | Text description of protocol deviation | String | |

Dataset name: diary.csv (one line per day per participant)

Source: Crying diaries, crude data reported hourly

Format: csv

Details for data format

| Variable | Source | Description | Type | Levels |
|----------|--------|--|------------|---------|
| id | diary | UID | Numerical | integer |
| h6 | diary | Crying time from 6AM to 7AM (mins) | Continuous | minutes |
| h7 | diary | Crying time from 7AM to 8AM (mins) | Continuous | minutes |
| h8 | diary | Crying time from 8AM to 9AM (mins) | Continuous | minutes |
| h9 | diary | Crying time from 9AM to 10AM (mins) | Continuous | minutes |
| h10 | diary | Crying time from 10AM to 11AM (mins) | Continuous | minutes |
| h11 | diary | Crying time from 11AM to 7AM (mins) | Continuous | minutes |
| h12 | diary | Crying time from 12AM to 7AM (mins) | Continuous | minutes |
| h13 | diary | Crying time from 1PM to 2PM (mins) | Continuous | minutes |

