This question asks about overall change in the infant's symptoms, from completely recovered to vastly worse. (Completely recovered, much improved, slightly improved, no change, slightly worse, much worse, vastly worse). These levels are coded numerically in an ordinal manner and are to be compared between groups using non-parametrical approaches.

Experience and satisfaction

Experience was measured using a 5-point likert scale from Very good, fairly good, neither good not bad, fairly poor and very poor.

Satisfaction was measured using a 5-point likert scale from Very satisfied, fairly satisfied, neither satisfied nor dissatisfied, fairly dissatisfied and very dissatisfied.

We also asked if the parent thought osteopathic care helped their baby using a yes, no or unsure response.

Unexpected and or Adverse events

We asked parents about additional care they may have administered to their infants and additional health care consultations they sought during the trial period as a proxy indicator of adverse events, and we also asked directly about any changes in symptoms that cause the parent concern. These included more distress, more crying, more unsettled, more vomiting, increased difficulty in feeding, sleeping and anything else (other).

Serious adverse events are reported by parents and managing osteopaths. These are assessed by the trial managing group and coded as for the reason for being a SAE and the estimated likelihood these are related to the treatment.

6. Randomisation

Block randomisation with variable block size of 4 and 6 generated by CastorEDC.

7. Sample size

From data collected during the pilot phase (n=13), we confirmed crying times as expected by Wolke et al. We estimate the average daily crying time over the two-week follow-up period to be of 120 minutes with a SD of 45 minutes. To detect a minimum of 30 minutes additional reduction in crying time between the intervention and control group with 90% power and a two-sided 5% significance level we would need 48 infants in each arm of the trial. If we allow for a 15% drop out we would need to randomise 112 infants, 66 in each arm of the trial. This sample size calculation is conservative because it disregards the fact that there are repeated measures in each infant and that the model will be corrected for the baseline crying time value. Thus, the actual power will be higher.

| Power | MCID (daily reduction in crying time in minutes) | | | |

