Checking assumptions for primary outcome

a) Assumptions for repeated measures random linear mixed effect

The following assumptions for repeated measures random linear mixed effect need to be tested:

- The explanatory variables are related linearly to the response.
- The errors have constant variance.
- The errors are independent.
- The errors are normally distributed.

A graphical representation will plot the residuals against group allocation. This can indicate if the model fits the data appropriately. The residuals will also be plotted in the order of days after treatment to see any indications of visible trend over time. The residuals will be plotted against the fitted values to test whether there is any non-constant error variance. Finally, a histogram with a normal probability plot and Wilk-Shapiro test will be used to test the assumption of normality for crying-time distribution in each group.

If the distribution of crying time is not Gaussian, then it will be categorised, and the distribution of the response variable will be considered as ordinal, and the link function is logit. When the assumptions for distribution of the residuals are not met, transformation is to be used to make the analysis possible.

b) Testing and accounting for trends over time

Three methods are used to investigate trend over time:

- a. Visual and statistical assessment of trend over time is to be made using fractional polynomials in regression analysis separately for each group.
- b. Repeated measures random linear mixed model is to be used to test interactions between group allocation and days of follow-up. This makes it possible to assess that group differences are constant through time. Explanatory variables are group allocation, interaction between group allocation and number of days of follow-up, baseline crying time day before treatment, infant age at entry, treatment expectations. Linearity of response for the explanatory variable is tested as trends over time using mixed regression analysis.
- c. Day to day means in each group will be calculated using Delta-method linear prediction with fixed portion. Furthermore, linear trend over time will be tested in each group by modelling day to day residuals within the model.

Assumptions are to be verified on the linearity of the progression through time. Transformation is to be used if linearity is not met.

Secondary outcomes analysis

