Mixed effect linear regression will be used to test continuous secondary outcomes. Categorical response variables using Likert scales (i.e. global change, parent satisfaction) will be considered as ordinal and non-parametrical tests (Mann Whitney U test) will be used to test between group differences. When possible (results from fractional polynomials), the outcome is to be dichotomised and the link function will be logit. Between group changes in parenting confidence score will compare changes from baseline by entering baseline score as an explanatory variable.

Proportion of participants who reported at least one adverse event will be compared between groups using a Fisher exact test. The same approach will be used to compare unexpected reactions (distress, crying, unsettled, vomiting, difficulties feeding, difficulties sleeping, other).

For cost of treatment, we will determine the mean number of treatments per infants in the trial and per group, the mean number of treatments will be multiplied by the average cost of an osteopathic treatment in UK pounds, determined by the latest data from the Institute of Osteopathy census.

Descriptive exploratory analysis

- Analyse trends over time using fractional polynomials.
- Adjust for osteopath level variables if between osteopath heterogeneity.

- Description of eventual correlation between years of experience and treatment effects (i.e. analyse of trend and comparison for cut-off at 3 or less years versus 4 or more).
- Investigate eventual association between post-graduate training and treatment outcome (interaction term).

Complementary confirmatory analysis

- A sensitivity analysis without imputed median values for crying times in time slots were parents reported crying will be run.
- A sensitivity analysis to adjust for recruiting site (ESO, UCO, Private practice, Swiss and Australian sites).
- A sensitivity analysis is planned to verify that the observed results hold in the worst- and best-case scenarios for missing data. The 25th and 75th percentile are to be used to replace missing data (25th for one group and 75th for the other) before running the primary analysis.
- If baseline imbalance (p -value <0.10) is observed, a secondary analysis with adjustment for these variables will be run to confirm results.

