* Adjusted for baseline crying time, infant age and prior expectations for osteopathic care

Table 3 Effects of treatment on other outcomes including undesirable events

| Outcomes | Test group (TTR) | Control group (GTR) | Between group difference* |
|--|---------------------|------------------------|------------------------------|
| | N=xx | N= xx | (CI 95%; P-value) |
| Parenting Confidence Score [0–45]; mean (SD) | | | |
| Perceived changes in symptoms; n(%) | | | |
| Completely recovered | | | |
| Much improved | | | |
| Slightly improved | | | |
| No change | | | |
| Slightly worse | | | |
| Much worse | | | |
| Vastly worse | | | |
| Weight changes over 14 days (kg); mean (SD) | | | |
| Satisfaction with received care; n (%) | | | |
| Very satisfied | | | |
| Fairly satisfied | | | |
| Neither satisfied nor dissatisfied | | | |
| Fairly dissatisfied | | | |
| Very dissatisfied | | | |
| Unexpected reactions; n(%) | | | |
| More distress | | | |
| Crying more | | | |
| More unsettled | | | |
| Vomiting more | | | |
| Increased feeding difficulties | | | |
| Increased difficulties sleeping | | | |
| Other | | | |
| Serious adverse events; n(%) | | | |
| Death | | | |
| Hospitalisation | | | |
| Long lasting morbidity | | | |
| Any | | | |

* P-values measured using likelihood ratio test in linear/logistic regression, Mann-Whitney U test for ordinal outcomes, Chi2 for categorical

Table 4 Number of sessions, advice given, additional treatment and effectiveness of blinding

| | Test group (TTR) N=xx | Control group (GTR) N= xx | Between group difference* |
|--|---------------------------|---------------------------------|------------------------------|
| | Mean (SD) | Mean (SD) | (CI 95%; P-value) |
| Number of sessions; mean (SD) | | | |
| Advices; n(%) | | | |
| Managing the baby's sleep pattern | | | |
| Managing the baby's feeding pattern | | | |
| Mother's diet | | | |
| Handling the baby | | | |
| Managing the baby's environment | | | |
| Parenting behaviour | | | |
| Reassure parent/guardian | | | |
| Other | | | |
| Medication and remedies; n(%) | | | |
| Prescribed medication | | | |
| Anti-gas drops | | | |
| Herbal supplements | | | |
| Probiotics | | | |
| Non-cow or anti-allergenic formula milk | | | |
| Omeprazol | | | |
| Other | | | |
| Additional care; n(%) | | | |
| General practitioner | | | |
| Accident and Emergency | | | |
| Unplanned hospital admission | | | |
| Another osteopath | | | |
| Paediatrician | | | |

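### The SAP dichotomises ordinal secondary outcomes on a results-dependent condition, with no cut point fixed and no statement of which p-value governs

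*SAP*

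**What the plan says.** Four places in the SAP bear on the ordinal secondary outcomes.

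- **Section 5, Global change.** The coded levels "are to be compared between groups using non-parametrical approaches". No dichotomy is mentioned. The paragraph on experience and satisfaction in the same section names no test.
- **Section 8, Secondary outcomes analysis.** Likert outcomes, with global change and parent satisfaction named, "will be considered as ordinal and non-parametrical tests (Mann Whitney U test) will be used to test between group differences". The next sentence reads: "When possible (results from fractional polynomials), the outcome is to be dichotomised and the link function will be logit".
- **Section 9, Table 3.** The dummy table has one row for each of the seven global-change levels and each of the five satisfaction levels, and no responder row. Its footnote reads: "P-values measured using likelihood ratio test in linear/logistic regression, Mann-Whitney U test for ordinal outcomes, Chi2 for categorical".
- **Section 8, Testing and accounting for trends over time.** This shows what fractional polynomials are for elsewhere in the plan: "Visual and statistical assessment of trend over time is to be made using fractional polynomials in regression analysis separately for each group".

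**The concern.** The dichotomisation sentence leaves four things open: when it is possible to dichotomise, which fractional-polynomial result decides this, where each scale is cut, and whether the logit model stands beside the Mann-Whitney test or takes its place.

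The stated condition cannot close these gaps. A fractional polynomial describes the shape of a relation with a continuous predictor, and the plan uses it for crying time across follow-up days. Global change and satisfaction are each recorded once, in the day-14 questionnaire, so there is no time trend to fit. Two analysts following this sentence could reach different cuts, or one could cut and the other not. If the plan's other use is the model, the inspection is made separately by group, which is the setting in which a cut can come to follow the treatment difference.

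At stake are the 5% level for two secondary outcomes and, if the logit model becomes the reported analysis, some of their power.

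**Working it through.** **Inputs from the SAP.**
- Global change (Section 3, castor.csv): "1=completely recovered, 2= much improved, 3= slightly improved, 4= No change, 5= Slightly worse, 6= Much worse, 7= vastly worse". Seven levels, so 7 - 1 = 6 possible cuts.
- Satisfaction (same table): "1=very satisfied, 2=fairly satisfied, 3=Neither satisfied nor dissatisfied, 4=fairly dissatisfied, 5=very dissatisfied". Five levels, so 5 - 1 = 4 possible cuts.
- Two-sided 5% level (Sections 7 and 8).
- 48 infants per arm before drop-out (Section 7). The planned total of 112 gives 112/2 = 56 per arm. The text's 66 per arm does not match that total, which is a separate matter.

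**The plan's own figure.** With a difference of 30, an SD of 45 and 90% power, n per arm = 2 × (1.960 + 1.282)² × 45²/30² = 2 × 10.51 × 2.25 = 47.3, rounded up to 48. This reproduces the SAP. It is used here only as the arm size. The SAP gives no error-rate or power figure specific to the ordinal outcomes.

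**Assumption.** The SAP gives no level frequencies, so even and skewed distributions were assumed, three for each scale length.

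**False positives.** 20,000 trials were simulated per setting with no treatment difference, at 48 and 56 per arm. Each possible cut was tested with the Pearson chi-square.

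| How the analysis is chosen | 7 levels | 5 levels |
|---|---|---|
| Mann-Whitney only | about 5% | about 5% |
| One cut fixed in advance (non-sparse) | about 5% | about 5% |
| Cut nearest the pooled median, group not used | about 5% | about 5% |
| Smallest p-value over cuts with at least 5 infants per side | 17-20% | 11-16% |
| Smallest p-value over all cuts | 19-22% | 13-16% |
| Better of Mann-Whitney and any cut with at least 5 per side | 17-21% | 11-16% |

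Over both scales the first three rows span 4.7-5.3%, 4.4-6.1% and 4.4-5.4%. If the only freedom is between Mann-Whitney and one fixed middle cut, the rate is 5.8-7.7%. With a further assumed seven-level distribution (0.15, 0.35, 0.25, 0.15, 0.05, 0.03, 0.02) and at least 10 infants required on each side, the best-cut rate at 48 per arm falls to about 15%. The range of 15-20% for seven levels therefore covers best-cut selection with sparse cuts excluded.

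With the logistic likelihood ratio test over all cuts, the rates are 21-30% (seven levels) and 15-20% (five levels). Part of that excess comes from sparse cuts, where even a single fixed cut can reject in about 8-9% of null trials. It is not used as the main figure.

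**Power.** With the last distribution above, 48 per arm and an assumed odds ratio of 2.5, Mann-Whitney has about 68% power. A fixed cut at much improved or better has about 57%. The loss is 68 - 57 = 11 points, or about 10 in round terms.

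**The case against.** The strongest reply is that a reader might infer more than the SAP says. Four such readings go too far.

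- **That the logit model replaces Mann-Whitney.** The sentence immediately before assigns Mann-Whitney, and Table 3 keeps all levels and that test. The dichotomised model may be additional. What stands is that its status is not stated.
- **That the cut is to be chosen from the treatment difference.** The parenthesis governs whether to dichotomise. How to cut is not described at all, and nothing orders a search for the smallest p-value.
- **That the 5% level is therefore lost.** A cut taken from pooled data holds it, so the upper rates are a worst case that the wording allows.
- **That Section 5 fixes a non-parametric test for every ordinal scale.** It does so for global change only. For satisfaction the tension lies within Section 8 and with Table 3.

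The plan also has safeguards. Groups are coded A and B, the analysis is to be precoded in a .do file before data collection, the TSC validates the final coding before group identity is revealed, and deviations are recorded. These limit freedom, but none names a cut. A two-sided p-value can be minimised over cuts without knowing which arm is A. A precoded file can hold only a rule that has been written down, and the SAP writes down no rule for the cut.

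**Conclusion.** The point holds as a gap in pre-specification and an internal conflict. The dichotomisation has a results-dependent trigger that cannot work for an outcome measured once, no cut point, and no stated rank against the Mann-Whitney test. This follows from the text and needs no simulation.

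The size depends on how the gap is filled. The false positive rate could lie anywhere from about 5% to about 15-20% for global change, or 11-16% for satisfaction. The loss of about 10 points of power arises only if the logit model takes the place of Mann-Whitney. All of these figures rest on assumed level distributions, and the power figure also on the assumed odds ratio of 2.5. The primary crying-time analysis is not touched by this sentence.

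**What to change.** In Section 8, delete the dichotomisation sentence together with its fractional-polynomial condition, and name Mann-Whitney as the single test for each ordinal outcome. Sections 5 and 8 and the Table 3 footnote then agree for these scales.

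The Table 3 column asks for a 95% confidence interval, which a Mann-Whitney p-value alone does not give. A proportional-odds model can supply an odds ratio with its interval. This addition is useful but not essential to closing the gap.

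If a responder summary is wanted, name one cut per outcome before any data by group are examined (for example, completely recovered or much improved for global change) and label it supportive.

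The cost is a change of SAP wording and, if the estimate is added, one extra model.

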- Analyse potential correlations between missing data in diary and overall summary measures.

Missing data for hourly entries will not be replaced (e.i. not missing total at random) unless parents did not report minutes in an explicit was. Graphical representations are replaced by estimates of hourly crying time. Reported crying within a hourly time slot without specification on the duration is replaced by the median observed crying time from other reported crying for that specific time slot (i.e. hour of the day and day of the trial).

Given the nature of the analysis, missing data within the diary will only reduce the power but should not affect the overall analysis.

For a diary to be considered, at least 7/14 days need to be filled in. Furthermore, best-case, and worst-case scenario will be simulated for the primary outcome implementing lowest and highest values for missing data (see sensitivity analysis).

Descriptive analysis

Descriptive statistics will be used to summarise the characteristics of participants in each arm of the trial. This will include baseline values, treatment schedules, compliance and follow-up. We will show number and percentage or mean and standard deviation for categorical and normally distributed continuous variables respectively. For data severely deviating from a normal distribution, we will present median and interquartile ranges. Probability of observed between groups difference will be provided using either Fisher's exact test, Chi2 test, and or Student's t-test.

Primary outcome analysis

We will analyse the primary outcome of crying time (e.i. individual daily measures of mean crying time in minutes) using random-effects multilevel linear regression. Crying time will be entered as the response variable (dependant) and the link function is identity. Therefore, lack of independence for measures from the same participant will be accounted for. To improve statistical power, the following explanatory variables are to be added to improve the modelling of the between-group differences

- baseline crying time (continuous),
- expectations from treatment (ordinal)
- and age of infants at entry (continuous).

To account for missing data, the data can be categorized and treated as nominal.

Results will be reported as between group difference in crying time in minutes with a 95% confidence interval. Statistical inference for significance of effects of the intervention will be calculated using Wald Chi² test.

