- A sensitivity analysis adjusting for number of sessions, counselling and adjunctive treatment will be done to verify that the observed differences are not due to imbalance in patient management other than the tested intervention.
- Per protocol analysis.

9. Results analysis

Provisional tables

Table 1 Baseline characteristics for each group. GTR=, TTR=, SD=standard deviation

| Characteristics | Test group (GTR) N=xx | Control group (TTR) N= xx | Group imbalance (p-values) |
|---|-----------------------------|---------------------------------|----------------------------------|
| Females; n (%) | | | |
| Age of infant; n (%) | | | |
| 1–14 days (1–2 weeks) | | | |
| 15–28 days (3–4 weeks) | | | |
| 29–42 days (5–6 weeks) | | | |
| 43–56 days (7–8 weeks) | | | |
| 57–70 days (9–10 weeks) | | | |
| 71–84 days (11–12 weeks) | | | |
| Infant weight in kg; mean (SD) | | | |
| At birth | | | |
| At baseline | | | |
| Excessive crying, distress or unsettlement prior 24h; mean (SD) | | | |
| Age of mother in years; mean (SD) | | | |
| Siblings; n (%) | | | |
| None | | | |
| 1 | | | |
| 2 | | | |
| 3 or more | | | |
| Co-parenting; n (%) | | | |
| Parenting Confidence Score; n (%) | | | |
| Non-clinical range (40 or more) | | | |
| Mild clinical range (36-39) | | | |
| Moderate clinical range (32-35) | | | |
| Severe clinical range (31 or less) | | | |
| Expected response to osteopathic care; n (%) | | | |
| Very well | | | |
| Well | | | |
| Unsure | | | |
| Not very well | | | |
| Not well | | | |
| Missing | | | |

* Significant group imbalance at baseline

Table 2 Effects of treatment on crying time in minutes

| Outcomes | Test group (TTR) N=xx | Control group (GTR) N= xx | Adjusted * between group difference | Unadjusted between group difference |
|----------------------------------|------------------------------|---------------------------------|--|--|
| | Mean (Std.Err) | Mean (Std.Err) | Mean (CI 95%; P-value) | Mean (CI 95%; P-value) |
| Mean daily crying time (minutes) | | | | |
| From day 1 to day 13 | | | | |
| From day 1 to day 6 | | | | |
| From day 7 to day 13 | | | | |
| Daily crying times (minutes) | | | | |
| Day before treatment | | | | |
| Treatment day | | | | |
| Days after treatment | | | | |
| Day 1 | | | | |
| Day 2 | | | | |
| Day 3 | | | | |
| Day 4 | | | | |
| Day 5 | | | | |
| Day 6 | | | | |
| Day 7 | | | | |
| Day 8 | | | | |
| Day 9 | | | | |
| Day 10 | | | | |
| Day 11 | | | | |
| Day 12 | | | | |
| Day 13 | | | | |

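### The best/worst-case check for missing data is defined in two ways, its quartile form does not bound a worst case, and a second confirmatory check adjusts for care given after randomisation

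*SAP*

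**What the plan says.** **Best and worst case.** In SAP section 8, *Missing data*, the scenarios for the primary outcome are built by "implementing lowest and highest values for missing data (see sensitivity analysis". The list referred to, *Complementary confirmatory analysis*, gives the aim as to "verify that the observed results hold in the worst- and best-case scenarios for missing data" and the rule as: "The 25th and 75th percentile are to be used to replace missing data (25th for one group and 75th for the other". The primary analysis is then rerun on the filled data. Neither place says whether an hour, a day or a whole diary is replaced, or whether the percentiles are pooled, by arm or by day.

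**Adjustment for other care.** The same list includes: "A sensitivity analysis adjusting for number of sessions, counselling and adjunctive treatment will be done". Its stated purpose is to show that the difference is not explained by imbalance in management other than the tested intervention. Section 2 shows when these variables are recorded: on the osteopath's form after each encounter, and on the parent questionnaire 14 days after randomisation. The primary model adjusts only for baseline crying time, expectations and age.

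**The concern.** The missing-data check carries weight. Section 8 asserts that gaps in the diary cost only power, and it excludes diaries with fewer than 7 of 14 days. The best/worst-case check is the only listed analysis that varies, by arm, the values assumed for missing crying time. If its two definitions lead to different conclusions, an analyst following the SAP can report that the result survives a worst case when only a moderate scenario was run.

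The second check has a different weakness. Sessions, advice and additional care come after allocation. A model that conditions on them no longer makes the comparison that randomisation protects, yet it is listed as confirming the primary result.

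**Working it through.** **Inputs (SAP section 7).**
- Outcome: "average daily crying time over the two-week follow-up period to be of 120 minutes with a SD of 45 minutes".
- Target effect 30 min, power 90%, two-sided alpha 5%, giving 48 per arm before loss.
- Loss and total: "If we allow for a 15% drop out we would need to randomise 112 infants, 66 in each arm of the trial". I use 56 per arm, since 112/2 = 56; the stated 66 does not fit a total of 112, which is a separate matter.

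**The plan's own figure.** n per arm = 2 × (1.960 + 1.282)² × 45² / 30² = 47.3, rounded up to 48. All 12 cells of the sample size table reproduce as 2n. Then 96/0.85 = 112.9, close to the stated 112.

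**Assumptions of mine.** SD 45 is the SD of infant means, because no day-level SD is given. Whole infants are filled; the version history speaks of missing diaries, but section 8 names no unit. Outcomes are normal, and a fraction d = 0.15 is missing in each arm. The observed difference (test minus control) is -30 min.

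**Fill gaps.**
- Quartiles: 2 × 0.6745 × 45 = 60.7 min.
- Lowest to highest, expected range of normal values: 4.46 × 45 = 201 min for 48 infants (by arm), or 4.99 × 45 = 224.5 min for 96 (pooled).

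**Worst-case difference.**
- Pooled percentiles: -(1 - d) × 30 + d × gap.
- Arm-specific percentiles: -30 + d × gap, because each fill value keeps its own arm's mean.

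| Rule | Arm-specific | Pooled |
|---|---|---|
| 25th/75th | -30 + 9.1 = -20.9 | -25.5 + 9.1 = -16.4 |
| Lowest/highest | -30 + 30.1 = +0.1 | -25.5 + 33.7 = +8.2 |

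**Pooled version at other missing fractions (quartile / lowest-highest).** 5%: -25.5 / -17.3; 10%: -20.9 / -4.6; 20%: -11.9 / +20.9 min.

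**Missing fraction at which the worst case reaches zero.**
- Pooled, 30/(30 + gap): 33% for quartiles, 12% for lowest/highest.
- Arm-specific, 30/gap: 49% and 15%.

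**Simulation.** 56 per arm, 8 missing per arm, pooled percentiles, true effect 30 min, t-test on infant means. The share of trials still significant in favour of the test arm was 0.91 on observed data, 0.51 under quartiles and 0.00 under lowest/highest. A normal curve can run below zero minutes, so this was repeated with gamma outcomes, which cannot: 0.89, 0.51 and 0.00.

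**Standard error after constant filling.** With 48 observed per arm, SE = √(2 × 2025/48) = 9.19. After filling, each arm's variance is 0.85 × 2025 + 0.85 × 0.15 × offset², divided by 56. The offset is the distance from the fill value to the arm's observed mean.
- Quartile, offset ignored: 7.84 (15% below 9.19).
- Quartile, offset 30.35: 8.10 (12% below).
- Quartile, pooled with the 30-min effect, offset 45.35: 8.42 (8% below).
- Lowest/highest at ±2 SD, offset 90: 9.92; with the 30-min effect, offset 105: 10.57. Both exceed 9.19.

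**Post-randomisation adjustment.** In a linear model with one added covariate M, adjusted difference = unadjusted difference - (slope of crying on M within arm) × (arm difference in M). The slope mixes any effect of M with causes shared by M and crying. The SAP gives neither factor, so the shift has no known size or sign. The SAP's own uses of these variables also tell against treating them as background. Section 5 takes additional care and consultations as a proxy for adverse events. Section 8 uses number of treatments for the cost result. In the test arm, sessions are how the tested intervention is delivered.

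**The case against.** The best defence is that these are not two rival analyses: *Missing data* gives a general description and sends the reader to the list, which holds the working rule. The cross-reference does make the quartile rule operative. It does not make a quartile a worst case, and the list still claims to verify worst and best cases.

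A reader might infer that the quartile rule is too mild to be useful. The figures do not support that: with pooled percentiles it takes the difference from -30 to -16.4 min and the share of significant trials from 0.91 to 0.51. Lowest/highest filling left no simulated trial significant at this loss, so preferring quartiles is defensible. Daily values vary at least as much as infant means, so daily quartiles would be at least as far apart.

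A reader might also infer that constant filling always makes the interval too narrow. That holds for quartile filling of whole infants but not for lowest/highest filling, where the SE rises.

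On the adjustment, the aim is sensible. Advice and support are meant to be common to both arms, the version history gives performance differences between groups as the reason, and the analysis is called a sensitivity analysis. It is tempting to add that sessions or counselling respond to how the infant is doing. The SAP does not say so, and section 8 speaks of planned treatments. The point does not need that inference: it is enough that these variables arise after allocation.

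**Conclusion.** The point stands as one of definition and labelling with a practical consequence. At the plan's own loss rate and effect, the worst-case difference is about -21 min (arm-specific) or -16 min (pooled) under quartiles, and about 0 or +8 min under lowest/highest. The conclusion that the result holds can therefore depend on the definition; it need not in every data set, and with little missing data both rules leave the sign unchanged. Under quartile filling of whole infants the SE is about 8 to 15% too small.

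These figures rest on SD 45 for infant means, normality, equal loss by arm and whole infants as the unit. The model adjusted for sessions, counselling and adjunctive treatment cannot deliver the verification claimed for it; how far and in which direction it would mislead is unknown. A reader might infer that the primary analysis is compromised. It is not: both items are secondary checks, and the primary model uses baseline covariates only.

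**What to change.** 1. State one definition in both *Missing data* and *Complementary confirmatory analysis*: the unit replaced (hour, day or diary), the source distribution (pooled, by arm or by day), and that both directions are run.
2. If quartiles are kept, call them a moderate scenario. Alternatively, replace them with a delta-shift or tipping-point analysis, for example after multiple imputation, that reports the shift at which the conclusion changes. Multiple imputation would also avoid treating filled values as observed.
3. Move the model adjusted for sessions, counselling and adjunctive treatment from the confirmatory list to *Descriptive exploratory analysis*, and drop the claim that it verifies the result. Rely on the by-arm reporting of these variables already planned in provisional Table 4 of section 9.

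Cost: SAP wording and a little extra analysis code. The data collected and the primary model stay as they are.
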